14.11 PUBLICATION POLICY

ObsEva registers clinical trials (Phase I – IV) wherever and whenever mandatory on publicly accessible websites (e.g.: www.clinicaltrials.gov ; www.clinicaltrialsregister.eu), including posting the trial design, population, and study details as required.

ObsEva posts the outcome of clinical trials on the required medium(a), within required timelines, regardless of the nature of the outcome.

ObsEva shares information on the outcome of clinical trials with the Principal/Coordinating Investigators of trials in the form of a final report synopsis, regardless of the trial outcome.

ObsEva duly communicates to stakeholders all relevant information arising from research activities related to products developed by the company, at any point and during any phase of the development of a product and the entire life-cycle of an ObsEva product.

Registration, reporting and communication of clinical trial results, results and/or outcome of non-clinical research are subject to mandatory preliminary review and authorization by the relevant ObsEva functions, prior to disclosure.

Appendix A. Schedule of study assessments – Screening and Treatment Periods

Schedule of study assessments – Screening and Treatment Periods								
Timing ¹	Screening Period (up to 3 months ²)	Treatment Period						
		Day 1	M1	M2	M3	M4	M5	M6
Informed Consent	X							
Inclusion-Exclusion criteria	X	X						
Demography, height, weight, medical history	X							X ³
mB&B	X							
Columbia-Suicide Severity Rating Scale	X	X	X	X	X	X	X	X

¹ All post-baseline visits should take place at the end of the defined period (i.e. M1 visit should be scheduled at the end of Month 1, M2 visit should be scheduled at the end of Month 2, etc.). Post-baseline visits dates are calculated from Day 1 visit date. A month is defined as 28 days/4 weeks. Visits should be scheduled \pm 3 days from the calculated date.

² If required for washout of oral contraceptives, other sex hormones, or GnRH antagonists/agonists (provided that the reason for discontinuing the previous GnRH-antagonist is not lack of efficacy), a period of up to 3 months is allowed between signing the informed consent and the screening visit.

³ Only weight will be recorded.

Schedule of study assessments – Screening and Treatment Periods								
Timing ¹	Screening Period (up to 3 months ²)	Treatment Period						
		Day 1	M1	M2	M3	M4	M5	M6
ECG	x	x ⁴	x	x	x	x	x	x
Physical examination	x				x			x
Vital signs	x	x	x	x	x	x	x	x
Urine pregnancy test	x	x	x	x	x	x	x	x
TVUS of uterus	x				x			x
Gynecological examination	x				x			x
Endometrial biopsy	x							x ⁵
Pap smear test	x							
Breast examination (mammogram if required)	x							x

⁴ ECG on Day 1 should be performed twice: once before treatment and once after treatment (just before PK sampling).

⁵ If endometrium thickness in TVUS is ≤ 5 mm, no endometrial biopsy will be necessary.

Schedule of study assessments – Screening and Treatment Periods								
Timing ¹	Screening Period (up to 3 months ²)	Treatment Period						
		Day 1	M1	M2	M3	M4	M5	M6
Clinical laboratory & urinary protein dipstick	x	x ⁶	x ⁶	x	x ⁶	x	x	x ⁶
Blood sample for PK ⁷		x	x	x	x	x	x	x
BMD by DXA	x							x
Adverse events	x	x	x	x	x	x	x	x
Previous/concomitant medication	x	x	x	x	x	x	x	x
Contraceptive dispensing and counselling	x	x	x	x	x	x	x	x
Permitted analgesic prescribing/dispensing	x	x	x	x	x	x	x	x
Vitamin D and calcium dispensing		x	x	x	x	x	x	x
Subject eDiary completion training/check	x	x	x	x	x	x	x	x

⁶ Overnight fasting is required.

⁷ PK samples should be taken after the ECG and before the daily dose of IMP, except on Day 1 when the PK sample should be taken at least 1.5 h after the IMP administration.

Schedule of study assessments – Screening and Treatment Periods								
Timing ¹	Screening Period (up to 3 months ²)	Treatment Period						
		Day 1	M1	M2	M3	M4	M5	M6
IMP accountability			x	x	x	x	x	x
Dispense study drug		x	x	x	x	x	x	
Dispense ABT		x			x			
EHP-30, EQ-5D-5L and PROMIS ⁸		x	x		x			x
mPGIS, PGIC, HRUQ and HRPQ		x ⁹	x	x	x	x	x	x
Specific monthly severity questions ⁸		x			x			x
SSIQ and PSIQ ⁸		x						x
AMH		x						
E2, LH, P4		x	x	x	x	x	x	x
SHBG		x			x			x
Bone biomarkers		x			x			x

⁸ ClinROs (Monthly dyspareunia question, PSIQ and HRUQ) will be administered to the subject by the site staff and the responses will be filled in the eDiary. ePROs (EHP-30, EQ-5D-5L, PROMIS, PGIS, PGIC, HRPQ and SSIQ, and specific monthly severity questions) will be filled in by the subject in the eDiary.

⁹ PGIC not done at Day 1.

Schedule of study assessments – Screening and Treatment Periods								
Timing ¹	Screening Period (up to 3 months ²)	Treatment Period						
		Day 1	M1	M2	M3	M4	M5	M6
Question regarding treatment received								x

Appendix B. Schedule of study assessments – Follow-up Period

Schedule of study assessments – Follow-up Period						
Timing¹	M1 FU	M2 FU	M3 FU	M4 FU	M5 FU	M6 FU
Previous/concomitant medication	X	X	X	X	X	X
Adverse events	X	X	X	X	X	X
Columbia-Suicide Severity Rating Scale	X	X	X	X	X	X
ECG	X		X			X
Physical examination			X			X
Weight						X
Vital signs	X		X			
Gynecological examination			X			

¹ All follow-up study visits should take place at the end of the defined period (i.e. M1 FU visit should be scheduled at the end of the first month of follow-up, M2 FU visit should be scheduled at the end of the second follow-up visit, etc.). A month is defined as 28 days/4 weeks. Visits should be scheduled \pm 7 days from the calculated date.

Schedule of study assessments – Follow-up Period						
Timing ¹	M1 FU	M2 FU	M3 FU	M4 FU	M5 FU	M6 FU
Breast manual examination			x			
Endometrium TVUS			x			x
Endometrial biopsy	x ²	x ²	x ²	x ²	x ²	x ³
Clinical laboratory & urinary protein dipstick	x		x ⁴			
Subject eDiary completion check	x	x	x	x	x	x
Subject eDiary collection and deactivation						x
EHP-30, HRUQ, HRPQ, EQ-5D-5L and PROMIS			x			x
mPGIS and PPGIC	x	x	x	x	x	x
BMD by DXA						x ⁵
E2, LH, P4	x		x			

² Endometrial biopsy will be taken only if diagnosis at preceding month was different than “benign endometrium” or if no endometrial biopsy was done at Month 6 nor at any visit since Month 6.

³ An end-of-study biopsy is mandatory if no endometrial biopsy was obtained at M6 nor at any of the subsequent monthly visits.

⁴ Overnight fasting is required.

⁵ Subjects with a BMD decrease from baseline of > 1.5% for lumbar spine and/or > 2.5% for total hip at Month 6 FU visit will have an additional DXA scan 6 months later.

Schedule of study assessments – Follow-up Period						
Timing ¹	M1 FU	M2 FU	M3 FU	M4 FU	M5 FU	M6 FU
FSH at local laboratory for subjects that do not resume menses at M3 FU visit			X			
Bone biomarkers			X			
Permitted analgesic prescribing/dispensing	X	X	X	X	X	
Vitamin D and calcium dispensing	X	X	X	X	X	
Urine pregnancy test and contraceptive dispensing and counselling	X	X	X			X

Appendix C. Modified Biberoglu & Behrman symptom severity scale*

A. Dysmenorrhea

- None 0 = No symptoms
- Mild 1 = Some loss of ability to work or carry out normal activities
- Moderate 2 = Unable to work or carry out normal daily activities for part of 1 or more days and/or moderately decreased work efficiency
- Severe 3 = Unable to work or carry out normal daily activities for 1 or more full days and/or significantly decreased work efficiency

B. Deep Dyspareunia

- None 0 = No symptoms
- Mild 1 = Tolerated discomfort during intercourse
- Moderate 2 = Interference of usual frequency of sexual intercourse due to pain
- Severe 3 = Avoids, or wishes to avoid, intercourse because of pain

C. Non Menstrual Pelvic Pain

- None 0 = No symptoms
- Mild 1 = Occasional pelvic discomfort
- Moderate 2 = Noticeable discomfort for most of cycle
- Severe 3 = Pain persistent during cycle other than during menstruation

Total Pelvic Pain Score (A + B + C)	
None	0
Mild	1 - 3

None	0
Mild	1 - 3

D. Pelvic Tenderness *(assessed by the physician)*

- None 0 = No findings
- Mild 1 = Minimal tenderness on palpation
- Moderate 2 = Moderate tenderness on palpation
- Severe 3 = Exam limited due to tenderness

Total Physical Sign Score (D + E)	
None	0
Mild	1 - 2

None	0
Mild	1 - 2

E. Induration *(assessed by the physician)*

- None 0 = No findings
- Mild 1 = Uterus freely mobile, minimal induration in the cul-de-sac
- Moderate 2 = Significant induration in the cul-de-sac, restricted uterine mobility
- Severe 3 = Nodular adnexa and cul-de-sac, uterus fixed

Composite Pelvic Pain and Physical Sign Score (A + B + C + D + E)	
None	0

None	0
------	---

Mild	1 - 2
Moderate	3 - 5
Severe	6 - 10
Very Severe	11 – 15

** based on Biberoglu KO, Behrman SJ. Dosage aspects of danazol therapy in endometriosis: short term and long term effectiveness. Am J Obstet Gynecol. 1981;139:645.*

Appendix D. Endometriosis Health Profile questionnaire (EHP-30)

Final English (US) EHP-30 + Section C

© Copyright, Oxford University Innovation Limited 2001. All Rights Reserved.

The authors, being [name], [name] and [name], have asserted their moral rights.

PART 1: CORE QUESTIONNAIRE

**DURING THE LAST 4 WEEKS,
BECAUSE OF YOUR ENDOMETRIOSIS, HOW OFTEN HAVE YOU...**

	Never	Rarely	Sometimes	Often	Always
1. Been unable to go to social events because of the pain?					
2. Been unable to do jobs around the house because of the pain?					
3. Found it difficult to stand because of the pain?					
4. Found it difficult to sit because of the pain?					
5. Found it difficult to walk because of the pain?					
6. Found it difficult to exercise or do the leisure activities you would like to do because of the pain?					

**DURING THE LAST 4 WEEKS,
BECAUSE OF YOUR ENDOMETRIOSIS, HOW OFTEN HAVE YOU...**

	Never	Rarely	Sometimes	Often	Always
7. Lost your appetite and/or been unable to eat because of the pain?					
8. Been unable to sleep properly because of the pain?					
9. Had to go to bed/lie down because of the pain?					
10. Been unable to do the things you want because of the pain?					
11. Felt unable to cope with the pain?					
12. Generally felt unwell?					
13. Felt frustrated because your symptoms are not getting better?					
14. Felt frustrated because you are not able to control your symptoms?					

**DURING THE LAST 4 WEEKS,
BECAUSE OF YOUR ENDOMETRIOSIS, HOW OFTEN HAVE YOU...**

	Never	Rarely	Sometimes	Often	Always
15. Felt unable to forget your symptoms?					
16. Felt as though your symptoms are ruling your life?					
17. Felt your symptoms are taking away your life?					
18. Felt depressed?					
19. Felt weepy/tearful?					
20. Felt miserable?					
21. Had mood swings?					
22. Felt bad-tempered or short-tempered?					

**DURING THE LAST 4 WEEKS,
BECAUSE OF YOUR ENDOMETRIOSIS, HOW OFTEN HAVE YOU...**

	Never	Rarely	Sometimes	Often	Always
23. Felt violent or aggressive?					
24. Felt unable to tell others how you feel?					
25. Felt others do not understand what you are going through?					
26. Felt as though others think you are whining?					
27. Felt alone?					
28. Felt frustrated that you cannot always wear the clothes you would choose?					
29. Felt your appearance has been affected?					
30. Lacked confidence?					

PART 2: MODULAR QUESTIONNAIRE CORRESPONDING TO SEXUAL RELATIONSHIPS

**DURING THE LAST 4 WEEKS,
BECAUSE OF YOUR ENDOMETRIOSIS, HOW OFTEN HAVE YOU...**

	Never	Rarely	Sometimes	Often	Always
1. Experienced pain during or after intercourse? If not applicable, please check here 					
2. Felt worried about having intercourse because of the pain? If not applicable, please check here 					
3. Avoided intercourse because of the pain? If not applicable, please check here 					
4. Felt guilty about not wanting to have intercourse? If not applicable, please check here 					
5. Felt frustrated because you cannot enjoy intercourse? If not applicable, please check here 					

Appendix E. PROMIS Fatigue – Short Form 6a

This scale is formally known as PROMIS Item Bank v1.0 – Fatigue – Short Form 6a. The questions and the response categories included in this scale are presented below.

Please respond to each question or statement by marking one box per row.

	During the past 7 days...	Not at all	A little bit	Somewhat	Quite a bit	Very much
1	I feel fatigued					
2	I have trouble starting things because I am tired					
In the past 7 days...						
3	How run-down did you feel on average?					
4	How fatigued were you on average?					
5	How much were you bothered by your fatigue on average?					
6	To what degree did your fatigue interfere with your physical functioning?					

Scoring Rules:

The mapping of the response categories is as follows:

1 = Not at all; 2 = A little bit; 3 = Somewhat; 4 = Quite a bit; 5 = Very much

Assessment will be based on the sum of the individual scores across the six questions (possible scores 6 to 30, 6 = not at all, 30 = very much). Missing data will not be imputed.

Appendix F. Health-Related Productivity Questionnaire (HRPQ)

Health Related Productivity Questionnaire V2 (Generic)

These questions deal with how illnesses and their treatment have affected your ability to remain in the workforce and perform work and daily activities in your home. Your responses and those of other patients will help us to understand the impact of illnesses and their treatment on these aspects of your life.

1. What is your **current** employment status?
- a. Currently employed full-time → Please go to Question 2
 - b. Currently employed part-time → Please go to Question 2
 - c. Not currently employed → Please go to Question 5

2. How many hours were you scheduled to work at your job during the last **week**?
(If none or you are not employed, put a "0" here and go to Question 5.)
- _____ Hours

3. Did **illnesses/treatments** keep you from working any of your scheduled hours during the last **week**?
- a. Yes → I missed _____ hours of work because of **illnesses/treatments**.
 - c. No, **illnesses/treatments** did not keep me from working my scheduled hours.

4. For the hours that you **did** work during the past week, how did **illnesses/treatments** impact your **work output**?

Write a number on the line below, based on this scale.	0%..... Illnesses/treatments had no impact on how much I accomplished100% Illnesses/treatments kept me from accomplishing anything
_____ % impact on work output		

5. How many hours of household chores (cooking, cleaning, gardening, repairs, etc.) did you plan to do during the last **week**?
(If none, put a "0" here and go to Question 8.)
- _____ Hours

6. Did **illnesses/treatments** keep you from doing any of your planned hours of household chores last **week**?
- a. Yes → I worked _____ hours less because of **illnesses/treatments**.
 - c. No, **illnesses/treatments** did not keep me from working my planned hours.

7. For the hours of household chores you **did** during the past week, how did **illnesses/treatments** impact your **work output**?

Write a number on the line below, based on this scale.	0%..... Illnesses/treatments had no impact on how much I accomplished100% Illnesses/treatments kept me from accomplishing anything
_____ % impact on work output		

.....
[This block of items deals with workforce participation and should be collected at study start]

8. How long has it been since [X] developed?

_____ Months _____ Years

9. Which of the following statements are true of your life since [X] developed (mark all that apply):

- [X] or its treatment(s) forced me to work part-time when I wanted to work **full-time**.
For how long was this true? _____ Months _____ Years
- [X] or its treatment(s) kept me from having a job when I wanted to work **full-time**.
For how long was this true? _____ Months _____ Years
- [X] or its treatment(s) kept me from having a job when I wanted to work **part-time**.
For how long was this true? _____ Months _____ Years
- None of the above

Appendix G. Health Resource Utilization Questionnaire (HRUQ)

(To be completed by Site Staff)

Subject number: _____

Study Visit (please ensure to tick 1 visit only):

Treatment period Day 1 Month 1 Month 2 Month 3
 Month 4 Month 5 Month 6

Follow-up period Month 3 FU Month 6 FU

Date of Assessment: _____

Instructions to complete:

At each scheduled on-site visit in the Treatment Period (Day 1 through Month 6) and at Month 3 FU and Month 6 FU visits in the Follow-up period, please ask if the subject saw a **non-study** health care practitioner since her last scheduled on-site visit for a **routine/general health care visit that is not associated with an adverse event**.

Only record below the health care visits with non-study health care practitioners. Any visits associated with Adverse Events should be recorded on the AE eCRF form only (do not record below).

Question 1

Since the subject's last scheduled study on-site visit, has she seen a **non-study** health care practitioner (e.g., physician, nurse practitioner, physician assistant, dentist, physical therapist) for a **routine/general health care visit that is not associated with an adverse event?**

No Yes *If Yes, please complete the questions 2 and 3 below.*

Question 2

- a. Select the type of non-study health care practitioner who saw the subject.
- b. Indicate if it was at an office or a clinic (includes a hospital outpatient visit)
- c. Indicate the number of times the subject was seen by each practitioner.

Types of non-study health care practitioner who saw the subject (check all that apply)	Type of facility		Number of times subject was seen by this non-study health care practitioner	
	Office	Clinic	Office	Clinic
 AUDIOLOGIST				
 ALLERGIST				
 CARDIOLOGIST				
 DENTIST				
 DERMATOLOGIST				
 ENDOCRINOLOGIST				
 ENT				
 FAMILY PHYSICIAN				
 GASTROENTEROLOGIST				
 GYNECOLOGIST				
 HEMATOLOGIST				
 HEPATOLOGIST				
 IMMUNOLOGIST				

 INFECTIOUS DISEASE SPECIALIST				
 INTERNAL MEDICINE SPECIALIST				
 INTERNIST				
 MEDICAL GENETICIST				
 NEPHROLOGIST				
 NEUROSURGEON				
 NURSE				
 NURSE PRACTITIONER				
 OCCUPATIONAL THERAPIST				
 OPHTHALMOLOGIST				
 ORTHOPEDIC SURGEON				
 OPTOMETRIST				
 PHYSIATRIST				
 PHYSICAL THERAPIST				
 PLASTIC SURGEON				
 PODIATRIST				
 PSYCHOLOGIST				
 PULMONOLOGIST				
 RADIOLOGIST				
 REPRODUCTIVE ENDOCRINOLOGIST				
 RHEUMATOLOGIST				
 SURGEON				
 UROLOGIST				
 UNKNOWN				
 OTHER HEALTH CARE PRACTITIONER (specify type):				

Question 3

Did the Subject have any diagnostic or therapeutic procedures performed by a non-study health care practitioner since the last scheduled study on-site visit?

No Yes *If Yes, complete question 4 below.*

Question 4

- a. Select the type of diagnosis/therapeutic procedures performed by non-study health care practitioner who saw the subject.
- b. Indicate the number of times the diagnosis/therapeutic procedures were performed.

Diagnostic/Therapeutic Procedure (check all that apply)		Number of times the procedure was performed
Ultrasound Scan		
Physical Examination		
Vital Signs		
MRI		
CT Scan		
X-Ray		
Biopsy and Histologic Examination		
Pelvic Exam		
Urine Test		
Blood Test		
Hysteroscopy		
SIS (Saline infusion Sonohysterography)		
Colposcopy		
Other (specify):		

Question 5

Has the patient spent any nights as a hospital in-patient since the last visit?

No

Yes

If Yes, how many nights did they spend in hospital?

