- Change from baseline to each scheduled assessment in the number of days of opioid analgesic use for EAP during the previous 4-week period as assessed in the eDiary
- Change from baseline to each scheduled assessment in the number of pelvic pain-free days (assessed on the VRS) during the previous 4-week period
- Change from baseline to each scheduled assessment in ability to perform daily activities during the previous 4-week period, as assessed in the eDiary (daily function NRS)
- Change from baseline to each scheduled assessment in the number of days with no difficulty in doing daily activities due to EAP during the previous 4-week period as assessed in the eDiary (daily function NRS)
- Change from baseline to each scheduled assessment in the number of days when dyspareunia was a problem during the previous 4-week period (including days when sexual intercourse was avoided because of anticipation of pain) as assessed on the dyspareunia VRS

- Change from baseline to each scheduled assessment in the number of days when sexual intercourse was avoided because of anticipation of pain during the previous 4-week period as assessed on the dyspareunia VRS
- Change from baseline to each scheduled assessment in the number of days with uterine bleeding (including spotting) during the previous 4-week period measured by eDiary
- Change from baseline to each scheduled assessment in the number of days when school or work was missed due to EAP in the previous 4-week period as reported in the eDiary
- Change from baseline to each scheduled assessment in the number of days when the subject had to go to bed or lie down due to EAP in the previous 4-week period as reported in the eDiary
- Change from baseline to each scheduled assessment in the Pain, Control and powerlessness, Emotional well-being, Social support, Self-image dimensions and the Modular sexual relationship questionnaire of EHP-30 scores
- Change from baseline to each scheduled assessment in the Health Related Productivity Questionnaire (HRPQ) scores
- Number of non-study endometriosis related health visits, number of days in hospital and type of procedures performed based on Health Resource Utilization Questionnaire (HRUQ) at each scheduled assessment
- Change from baseline to each scheduled assessment in the Physician/Subject Surgery Intention Question (PSIQ/SSIQ)
- Change from baseline to each scheduled assessment in the PROMIS Fatigue – Short Form 6a

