10.2.1 Screening Period – Screening visit

The subject will be informed of the study objectives and overall requirements, and written informed consent will be obtained before performing any study-specific procedures that are not standard of care.

The subject will be considered as included into the study after the ICF is signed and dated by the subject and the Investigator or legally acceptable designee.

For subjects who require washout for oral contraceptives, or other sex hormones, or GnRH antagonists/agonists (provided that the reason for discontinuing the previous GnRH-antagonist is not lack of efficacy), a period of up to 3 months will be allowed between signing the ICF and starting the collection of pain assessments in eDiary during the screening period. The screening period must cover

two full menstrual cycles and will last about 3 months. During the screening period, the subject will be seen up to three times if not all screening assessments could be performed at the first screening visit (e.g. the endometrial biopsy must be performed after day 7 of the menstrual cycle).

During the screening period the following study screening assessments will be completed (see Schedule of Assessments in Appendix A):

- Demographic data, height and weight
- Medical and surgical history including concomitant diseases (and especially presence of rectovaginal endometriosis and adenomyosis), previous medication, obstetric/gynecological history and history of endometriosis including diagnosis and previous treatments for endometriosis.
- Assessment of DYS, dyspareunia and NMPP with the mB&B scale (see Appendix C). Answers will be captured in eCRF.
- Completion of the paper C-SSRS questionnaire “Baseline” version specific for subjects under screening (see Appendix R)
- ECG
- Physical examination
- Vital signs (blood pressure (BP) and heart rate)
- Urine pregnancy test
- TVUS of uterus and ovaries to measure endometrial thickness, to rule out any clinically significant gynecological conditions which might interfere with the study efficacy and safety objectives and to confirm that the subject has no ovarian endometrioma ≥ 7 cm in diameter
- Gynecological examination, including the mB&B scale (see Appendix C) clinical signs reporting (pelvic tenderness and pelvic induration)

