10.3.3.4 Health Resource Utilization Questionnaire (HRUQ)

The HRUQ records use of health resources (emergency room, physician visit, hospitalization, etc.) during the study. This includes the number of non-study health visits – the total, the reason, primary reason, and type of clinician for the visit; Diagnostic/therapeutic procedures performed (Hysteroscopy, SIS, Colposcopy, Biopsy, Ultrasound or Other) and Emergency Room/Outpatient Procedures (see Appendix G).

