12.1.4 Exacerbation of endometriosis

In this protocol, symptoms and signs of exacerbation or worsening of endometriosis will usually be captured in the context of efficacy assessment. Therefore, symptoms, exacerbation or worsening of endometriosis will NOT be considered as AEs nor captured on the AE page of the eCRF unless clinically significant AND not consistent with the anticipated natural progression of the disease.

Lack of efficacy of the study drug is NOT considered as an AE.

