- Percent of scheduled work lost due to presenteeism (Number of hours lost/Number of scheduled hours*100)
- Percent of scheduled work lost in total (Number of hours lost/Number of scheduled hours*100)
- For "Household" group:
 - Number of hours household work lost due to absenteeism ("How many hours of work did you miss because of illnesses/treatments the last week?")
 - Number of hours household work lost due to presenteeism ("For the hours of household chores that you did during the past week, how did illnesses/treatments impact your work output?")
 - Total number of hours of household work lost
 - Percent of scheduled household work lost due to absenteeism (Number of hours lost/Number of scheduled hours*100)
 - Percent of scheduled household work lost due to presenteeism (Number of hours lost/Number of scheduled hours*100)
 - Percent of scheduled household work lost in total (Number of hours lost/Number of scheduled hours*100)

The change from baseline in the percentage of scheduled work lost due to absenteeism/presenteeism/total for employed and household groups will be analyzed with an analysis of covariance.

4.6.4.21. Number of non-study endometriosis related health visits, number of days in hospital and type of procedures performed based on Health Resource Utilization Questionnaire (HRUQ) at each scheduled assessment

The number of non-study endometriosis related health visits, number of subjects by type of clinician/clinic visit, number of subjects by type of therapeutic procedures, and number of nights spent in hospital will be summarized at each visit (Day 1, Month 1, Month 2, Month 3, Month 4, Month 5, Month 6). In case of many clinician/clinic types and therapeutic procedures, types may be regrouped for the descriptive summaries.

The change from baseline of number of non-study endometriosis related health visits and number of nights in hospital will be analyzed with a negative binomial model, including baseline as a covariate. The estimated least square means treatment differences along with 97.5% CI will be provided.

Sponsor:	ObsEva		
Protocol:	18-OBE2109-003		
Document Version No.:	V5.0	Document Date:	13-JUN-2022

4.6.4.22. Change from baseline to each scheduled assessment in the Physician/Subject Surgery Intention Question (PSIQ/SSIQ)

The PSIQ/SSIQ answers will be summarized as continuous at Day 1 and Month 6. Comparison between treatment arms at Month 6 will be done using analysis of covariance.

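### The printed HRUQ form cannot pick out endometriosis-related visits, the SAP has no rule for doing so, and Day 1 recall differs in length from the monthly visits

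*Protocol*

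**What the plan says.** Protocol 7.1.2.2 lists as an additional secondary endpoint "Number of non-study endometriosis related health visits, number of days in hospital and type of procedures performed", taken from the HRUQ at each scheduled assessment. SAP 4.6.4.21 adds an analysis: "The change from baseline of number of non-study endometriosis related health visits and number of nights in hospital will be analyzed". The model named there is negative binomial, and baseline is a covariate. Its HRUQ summaries are listed for Day 1 and Months 1 to 6.

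Three places describe the instrument:

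- **Protocol Appendix G** prints five questions. Question 1 asks whether, since the last scheduled on-site visit, the subject saw an outside practitioner for a "routine/general health care visit that is not associated with an adverse event". Practitioner types, counts, procedures and in-patient nights follow.
- **Protocol 10.3.3.4** says that the HRUQ records "the total, the reason, primary reason, and type of clinician for the visit".
- **SAP 4.2.8.3** gives cleaning rules for an eDiary HRUQ with items numbered up to at least 9.

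Two other sections matter. Protocol 12.1.4 says that "symptoms, exacerbation or worsening of endometriosis will NOT be considered as AEs nor captured on the AE page of the eCRF", except when the worsening is both clinically significant and out of keeping with the disease's expected course. Protocol 10.2.1 says that the screening period must cover "two full menstrual cycles and will last about 3 months", with up to three screening visits.

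**The concern.** The label and the measurement do not match. A form that counts dental and optometry check-ups, and does not ask why the woman went, gives an all-cause count. Such visits dilute any effect on endometriosis care, and a report table headed endometriosis related would mislead its reader. The visits of most interest, such as an unplanned visit to an outside gynecologist for a pain flare, are not clearly routine and are usually not adverse events, so site staff may record them in neither place.

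The second problem is the length of time each questionnaire covers. The SAP summarises and analyses change from baseline in a raw count, but the Day 1 count and the monthly counts can cover very different numbers of days. At stake is the resource-use part of the pharmacoeconomic objective.

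**Working it through.** The documents give no figure for this endpoint, so there is none to reproduce. The check compares the sections and then does the recall arithmetic.

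**Attribution**

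1. Appendix G: the practitioner list runs from audiologist to urologist and includes dentist and optometrist. There is no reason field for a visit, a procedure or a hospital night.
2. Protocol 10.3.3.4: reason and primary reason are recorded. This contradicts the printed form.
3. SAP 4.2.8.3: one trigger item (1) governs items 2 to 6 and another (7) governs items 8 and 9. The content of items 2 to 6 is not given, so the rules neither show nor exclude a reason item. They do show that the fielded numbering differs from Appendix G.
4. SAP 4.6.4.21: the outputs are visit counts, subjects by clinician or clinic type, subjects by procedure type, and nights. No step classifies a visit as endometriosis related, whether or not a reason was collected.

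**Recall length**

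Inputs: visits are every 28 days with a window of ±3 days (Protocol 10.2); the two screening cycles total 42 to 76 days (inclusion criterion 8); screening lasts about 3 months, taken as 3 × 28 = 84 days.

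- On treatment, recall is nominally 28 days, at most 28 - 6 = 22 to 28 + 6 = 34 days. It is nominally equal across Months 1 to 6.
- At Day 1 with a single screening visit at the start, recall is 42 to 84 days, or 42/28 = 1.5 to 84/28 = 3.0 times the treatment window. A later screening visit shortens it.

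At a constant rate of r visits per 28 days, the expected count over L days is r × L/28. With Day 1 recall of L days and 28 days on treatment, the relative change with no true effect is 28/L - 1, whatever r is. The counts below assume r = 0.5, because the documents give no rate.

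| Day 1 recall (days) | Expected Day 1 count | Expected monthly count | Apparent change |
|---|---|---|---|
| 14 | 0.25 | 0.5 | +100% |
| 28 | 0.50 | 0.5 | 0% |
| 42 | 0.75 | 0.5 | -33% |
| 76 | 1.36 | 0.5 | -63% |
| 84 | 1.50 | 0.5 | -67% |

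**Effect on the arm comparison**

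A simulation with no treatment effect (300 runs, 150 per arm, gamma-Poisson counts, assumed mean 0.5 visits per 28 days) fitted a negative binomial model to the post-baseline count with baseline as covariate.

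| Day 1 recall (days) | Mean log rate ratio (Monte Carlo SE) | Mean change in visits | Share of changes below zero |
|---|---|---|---|
| 28 | -0.007 (0.011) | 0.00 | 21% |
| 84 | -0.004 (0.011) | -0.99 | 50% |

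The treatment contrast stays at zero within simulation error. The within-group change does not. A negative binomial model cannot take the negative changes as outcomes, so the analysis cannot be run literally as SAP 4.6.4.21 words it.

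**The case against.** The strongest reply is that nothing proves the information is missing. Protocol 10.3.3.4 says reasons are recorded, and the eDiary form is numbered differently from Appendix G, so a reason item may have been fielded. That stands. A reader might infer that the endpoint cannot be obtained at all, but the documents do not support this. They show an unreconciled contradiction and a missing derivation rule. If a reason item exists, an all-cause relabelling would discard useful data, so the reconciliation must come first.

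A second reply is that recall length is the same by design in all randomised arms. That also stands: the distortion affects the within-group change, not the treatment contrast. Nor does the change always fall, since a screening visit less than 28 days before Day 1 reverses the sign.

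A reader might also infer that flare visits are certainly lost. Appendix G separates visits by adverse-event status, and staff could record a flare that is not an adverse event. The loss is a plausible risk that comes from the routine-visit wording, not a fact.

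Finally, a reader might object that the HRUQ is done in follow-up only at Month 3 FU and Month 6 FU, leaving gaps. This touches no planned HRUQ summary: the objective is limited to the Treatment Period and SAP 4.6.4.21 lists only Day 1 to Month 6.

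The SAP does already summarise subjects by clinician type, but that gives numbers of subjects, not numbers of gynecologist visits.

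**Conclusion.** The point holds as a mismatch between endpoint, form and analysis rule. With the printed form and the SAP as written, all-cause routine visits would appear under an endometriosis label. The raw within-group change from baseline is distorted by about -33% to -67% at a constant rate with 42 to 84 days of Day 1 recall. That range assumes one screening visit at the start of screening; the actual recall lengths are not known from the documents. The randomised comparison of post-baseline counts with baseline as covariate is not biased.

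The change from baseline is a SAP analysis; the protocol endpoint is the count at each assessment. This is an additional secondary endpoint outside the fixed-sequence testing, so the co-primary and ranked secondary conclusions and the type I error are unaffected.

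**What to change.** 1. Reconcile Protocol 10.3.3.4, Appendix G and SAP 4.2.8.3 against the form that was actually fielded.
2. If a reason item was fielded, state in SAP 4.6.4.21 that only visits whose primary reason is endometriosis are counted. If not, relabel the endpoint *all-cause non-AE health visits*, label nights and procedures as all-cause, and show the number of gynecologist visits separately.
3. Express Day 1 and monthly values per 28 days, using the actual days since the previous on-site visit. This also covers on-site visits replaced by telephone calls during COVID-19 (SAP 4.6.5.4).
4. Model the post-baseline count, not the change, in the negative binomial model, with log recall days as offset and the baseline rate as covariate. The sample code in SAP 4.6.4.3 already takes a count as its outcome.
5. For any further use of the form, drop the restriction to routine or general visits, add a yes/no item *mainly because of endometriosis*, and ask about the past 28 days at Day 1.

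The cost is minor SAP work and, without a reason item, a less specific label. Step 5 cannot alter treatment-period data already collected. If the Month 6 results have been released to the sponsor, steps 2 to 4 should be reported as changes made after unblinding.
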